4.1. Inclusion Criteria

Each potential subject must satisfy all of the following criteria to be enrolled in the study.

- 1. Subjects must be age 2 years to less than 18 years with a body weight >15 kg at the time of screening and at Week 0.
- 2. Diagnosis must be made per JIA ILAR diagnostic criteria and the onset of disease must have been before the subject's 16th birthday.
- 3. Active JIA of one of the following subtypes:
 - a. Rheumatoid factor positive or negative pJIA for ≥3 months prior to screening, or
 - b. Systemic JIA with no systemic symptoms for ≥3 months, but with polyarthritis for >3 months prior to screening, or
 - c. Extended oligoarticular JIA ≥ 3 months prior to screening, or
 - d. Polyarticular juvenile psoriatic arthritis ≥3 months prior to screening, or,
 - e. Enthesitis-related arthritis ≥3 months prior to screening.
- 4. Failure or inadequate response to at least a 2-month course of MTX before screening.
- 5. Subjects must have ≥5 joints with active arthritis at screening and at Week 0 as defined by ACR criteria (ie, a joint with either swelling, or in the absence of swelling, limited range of motion associated with pain on motion or tenderness).
- 6. Subjects must have a screening CRP of ≥ 0.1 mg/dL with the exception of approximately 30% of the study population.

- Subjects must have active pJIA despite current use of oral, intramuscular, or subcutaneous MTX for ≥ 2 months before screening. For subjects with BSA $< 1.67 \text{ m}^2$, the MTX dose must be between 10 to 30 mg/m² per week and stable for ≥ 4 weeks before screening. For subjects with BSA $\geq 1.67 \text{ m}^2$, the MTX dose must be a minimum of 15 mg/week and must be stable for ≥ 4 weeks before screening. In situations where there is documented intolerance of doses $> 10 \text{ mg/m}^2$ weekly (for subjects with BSA $< 1.67 \text{ m}^2$) or $\geq 15 \text{ mg/week}$ (for subjects with BSA $\geq 1.67 \text{ m}^2$); or where documented country or site regulations prohibit use of $\geq 15 \text{ mg}$ of MTX per week in subjects with BSA $\geq 1.67 \text{ m}^2$, subjects may be entered into the trial on a lower dose of MTX.

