 - d. Platelets $\ge 140 \times 10^3 \text{ cells/}\mu\text{L}$ (SI: $\ge 140 \times 10^9 \text{ cells/L}$)
 - e. Serum transaminase levels not exceeding 1.2 x the upper limit of normal for the central laboratory:
 - Aspartate aminotransferase (AST)
 - \circ \leq 67 IU/L (girls, ages 2 to \leq 4)
 - \circ \leq 58 IU/L (girls, ages 4 to \leq 7)
 - $\circ \leq 48 \text{ IU/L (girls, ages 7 to 18)}$
 - \circ \leq 83 IU/L (boys, ages 2 to \leq 4)

- \circ \leq 71 IU/L (boys, ages 4 to \leq 7)
- $\circ \leq 48 \text{ IU/L (boys, ages 7 to 18)}$
- Alanine aminotransferase (ALT)
 - $\circ \leq 41 \text{ IU/L (girls, ages 2 to 18)}$
 - \circ \leq 41 IU/L (boys, ages 2 to \leq 10)
 - $\circ \le 52 \text{ IU/L (boys, ages 10 to 18)}$
- f. Serum creatinine not to exceed:
 - 0.5 mg/dL (SI: 44 μ mol/L; ages 2 to 5)
 - 0.7 mg/dL (SI: 62 μmol/L; ages 6 to 10)
 - 1.0 mg/dL (SI: 88 μmol/L; ages 11 to 12)
 - 1.2 mg/dL (SI: 106 μmol/L; ages ≥13)
- 16. Subjects must be up to date with all immunizations in agreement with current local immunization guidelines for immunosuppressed subjects before Week 0.
- 17. A parent or guardian should accompany the subject to each study visit until the subject reaches the age of 18 years.
- 18. The subject and his/her parent (if applicable) must be able to adhere to the study visit schedule, and understand and comply with other protocol requirements.
- 19. Subject must be willing and able to adhere to the prohibitions and restrictions specified in this protocol.
- 20. Each subject (or their legally acceptable representative) must sign an ICF indicating that he or she understands the purpose of and procedures required for the study and are willing to participate in the study. Assent is also required of children capable of understanding the nature of the study (typically 7 years of age and older and per local regulations) as described in Section 16.2.3, Informed Consent.

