- 40. Subject has any condition for which, in the opinion of the investigator, participation would not be in the best interest of the subject (eg, compromise the well-being) or that could prevent, limit, or confound the protocol-specified assessments.
- 41. Subject is a girl who is pregnant, or breast-feeding, or planning to become pregnant while enrolled in this study or within 6 months after the last dose of study drug.
- 42. Subject is a boy who plans to father a child while enrolled in this study or within 6 months after the last dose of study drug.
- 43. Subject is unable or unwilling to undergo multiple venipunctures because of poor tolerability or lack of easy access.
- Subject is an employee of the investigator or study site, with direct involvement in the proposed study or other studies under the direction of that investigator or study site, as well as family members of the employees or the investigator.
- 45. Subject has active uveitis within 3 months prior to screening.
- 46. Subject with BSA $> 3.0 \text{ m}^2$.

NOTE: Investigators should ensure that all study enrollment criteria have been met at screening. If a subject's status changes (including laboratory results or receipt of additional medical records) after screening but before the first dose of study drug is given such that he or she no longer meets all eligibility criteria, then the subject should be excluded from participation in the study. Section 17.4, Source Documentation, describes the required documentation to support meeting the enrollment criteria.

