4.1. Demographics and Baseline Characteristics

The baseline measurement is defined as the closest measurement taken prior to the first study agent administration (Week 0) unless otherwise stated.

Subjects' demographic data including age, race, gender, height, weight, BSA, and BMI at baseline will be summarized. Baseline disease characteristics including duration of disease and baseline JIA efficacy assessments will be summarized.

Baseline TB information and medication usage will also be summarized.

The number of subjects will also be summarized by geographic region, country, and investigational site.

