6.3. Clinical Laboratory Tests

The laboratory parameters include but are not limited to the following:

Hematology: hemoglobin, hematocrit, neutrophils, lymphocytes, monocytes, eosinophils, platelets, and WBC count.

Chemistry: BUN/urea, creatinine, total bilirubin, alkaline phosphatase, ALT/SGPT, AST/SGOT, bicarbonate, sodium, potassium, calcium, albumin, chloride, phosphate, glucose, uric acid and total protein.

Laboratory results will be graded according to NCI-CTCAE version 4.03 or later. Note that toxicity grading for creatinine increase will be based on the NCI CTC v4.03 or later criteria, but limited only to the part based on the upper limit of normal (ULN), the other part, that is based on change from baseline, will not be used for toxicity grading. Generic normal ranges will be applied whenever reference ranges are not available.

17

NCI-CTCAE grades will be used in the summary of laboratory data (Grade 0-4). The proportion of subjects for select laboratory parameters with maximum Grades will be presented. In addition, the proportion of subjects with markedly abnormal laboratory results will also be provided. The subjects' maximum post-baseline ALT and AST will also be summarized by TB prophylaxis (TB prophylaxis, or no TB prophylaxis).

Levels of laboratory values that are considered to be markedly abnormal have been defined for each laboratory parameter in Attachment 3.

Boxplots will be used to describe the selected laboratory analyte at baseline and at each scheduled time point. The selected laboratory analytes are: WBC counts, neutrophils, hemoglobin, platelets, ALT, and AST.

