Attachment 3: Markedly Abnormal Laboratory Parameter Criteria

Table 3 Markedly abnormal criteria for laboratory parameters			
Hematology Test	Criteria for Markedly Abnormal Status		
Hemoglobin (g/L)	Decrease > 20.0 AND Value < 100.0		
Hematocrit (%)	Value < 0.27		
Total WBC (x10 ⁹ /L)	Value < 2.0 OR Value > 20.0		
Neutrophils, absolute (x10 ⁹ /L)	Percent decrease ≥33 AND Value < 1.5		
Lymphocytes, absolute (x10 ⁹ /L)	Percent decrease ≥ 33 AND Value < 1.5		
Eosinophils, absolute (x10 ⁹ /L)	Percent increase ≥ 100 AND Value > 1.3		
Platelet count (x10 ⁹ /L)	Percent decrease ≥50 AND Value < 75		
Chemistry Test	Criteria for Markedly Abnormal Status		
Alkaline phosphatase (U/L)	Percent increase ≥ 100 AND Value > 500		
ALT (U/L)	Percent increase ≥100 AND Value > 150		
AST (U/L)	Percent increase ≥ 100 AND Value > 150		
Total bilirubin (umol/L)	Percent increase ≥ 100 AND Value > 51.3		
Sodium (mmol/L)	(Increase ≥10 AND Value > 150) OR (Decrease ≥ 10 AND Value < 120)		
Potassium (mmol/L)	(Increase ≥ 0.8 AND Value > 5.5) OR (Decrease ≥ 0.8 AND Value < 3.0)		
Chloride (mmol/L)	Value < 85 OR Value > 120		
BUN/Urea (mmol/L)	Percent increase ≥ 66 AND Value > 14.28		
Creatinine (umol/L)	Percent increase ≥ 66 AND Value > 132.6		
Albumin (g/L)	Decrease ≥ 10.0 AND Value < 30.0		
Total protein (g/L)	Value < 45 OR Value > 100		
Calcium (mmol/L)	(Increase ≥ 0.37 AND Value > 2.62) OR (Decrease ≥ 0.37 AND Value < 1.87)

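### The markedly abnormal creatinine flag uses one absolute limit for ages 2 to 17, so children entering at 2–5 or 6–10 years need at least a 3.01-fold or 2.14-fold rise to be flagged

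*SAP*

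**What the plan says.** SAP 6.3 places the definitions in one attachment: "Levels of laboratory values that are considered to be markedly abnormal have been defined for each laboratory parameter in Attachment 3". The creatinine row there, in µmol/L, reads "Percent increase ≥ 66 AND Value > 132.6". It has no age bands. SAP 6.3 reports the proportion of subjects meeting the criteria, and Protocol 11.7 adds a listing of those subjects.

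The population is wide in age. Protocol 4.1, criterion 1: "Subjects must be age 2 years to less than 18 years with a body weight >15 kg". Criterion 15f, headed "Serum creatinine not to exceed", then sets four age-specific ceilings: 44 µmol/L (ages 2–5), 62 (ages 6–10), 88 (ages 11–12) and 106 (ages 13 and over).

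SAP 6.3 also grades laboratory values by NCI-CTCAE. For creatinine it keeps only the part defined against the upper limit of normal and drops the part defined against baseline. Generic normal ranges are used where reference ranges are not available.

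**The concern.** The two conditions are joined by AND, so the stricter one decides. With one absolute limit for all ages, the stricter one depends on where the subject starts, and the protocol's own entry caps show that younger children start much lower. For them the absolute limit always governs and the relative condition does no work.

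At stake is what the markedly abnormal proportion and listing can show about renal laboratory changes in the youngest subjects. A tripling of creatinine in a young child could be absent from both. No other planned creatinine categorisation measures the size of a rise from baseline, because that part of the CTCAE grading is switched off. SAP 1.4 names information on the safety profile in children as one consideration behind the sample size.

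**Working it through.** **Inputs.** Relative condition: rise of at least 66%, that is, a ratio to baseline of at least 1.66 (SAP Attachment 3). Absolute condition: value above 132.6 µmol/L (SAP Attachment 3). Highest permitted screening values: 44, 62, 88 and 106 µmol/L (Protocol 4.1, criterion 15f). The plan states no figure of its own to reproduce.

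**Formula.** Minimum fold rise to be flagged = max(1.66, 132.6 / baseline).

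**At the entry caps:**

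| Age at entry | Cap (µmol/L) | 132.6 / cap | Minimum fold rise | Value after a 66% rise from the cap | Flagged? |
|---|---|---|---|---|---|
| 2–5 | 44 | 3.01 | 3.01 | 73.0 | No |
| 6–10 | 62 | 2.14 | 2.14 | 102.9 | No |
| 11–12 | 88 | 1.51 | 1.66 | 146.1 | Yes |
| ≥13 | 106 | 1.25 | 1.66 | 176.0 | Yes |

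The cap is the highest eligible value, so 3.01 and 2.14 are the smallest rises that can be flagged in the two younger bands. Lower baselines need more: 132.6/35 = 3.79 and 132.6/25 = 5.30.

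**Where the 66% condition decides alone.** This needs 1.66 × baseline ≥ 132.6, so baseline ≥ 132.6/1.66 = 79.9 µmol/L. The caps of 44 and 62 rule this out at entry for ages 2–10.

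**Example.** A 4-year-old going from 40 to 120 µmol/L triples (120/40 = 3.00) but stays below 132.6 and is not flagged. The rise needed is 132.6/40 = 3.32-fold.

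**Does the screening cap carry over to baseline?** SAP 4.1 takes the last value before the first dose, which may be the Week 0 sample. The note closing Protocol 4.2 covers a change in status, laboratory results included, between screening and first dose: if the child "no longer meets all eligibility criteria, then the subject should be excluded from participation in the study". The cap therefore carries over for results known before dosing. For a Week 0 result known only afterwards to bring the 66% condition into play, it would have to be 79.9/44 = 1.82 or 79.9/62 = 1.29 times the cap.

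**How many subjects.** Protocol 3.1 expects about 10% of about 120 subjects aged 2 to 6 (0.10 × 120 = 12) and about 20% aged 6 to 12 (0.20 × 120 = 24). Up to about 36 subjects are affected, less any aged 11.

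**The case against.** The strongest reply is that this is one descriptive table among several safeguards. Protocol 11.7 plans cross-tabulations before versus after treatment by normal-range class, plus frequency tabulations of abnormalities. SAP 6.3 grades creatinine against the ULN. Protocol 9.4 has investigators review each laboratory report and record clinically relevant changes as adverse events. SAP 3.2 has an internal committee review laboratory data (the current Protocol 11.9 names the medical monitor and an internal safety team). The example child ends at 120/44 = 2.7 times the entry cap and, with an age-appropriate range, would show as above normal and be graded.

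Much of that stands, with limits. Neither document says the creatinine ULN is age-specific. Maximum grades are promised only for selected parameters, creatinine is not among the six boxplot analytes, and a normal-range class does not show how large a rise was.

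Three stronger readings are tempting and are not supported:

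- *Adolescents are generally flagged at 1.66-fold.* This holds only from a baseline of 79.9 µmol/L. An adolescent at 60 needs 2.21-fold and one at 50 needs 2.65-fold.
- *The reported proportion is biased or falsely reassuring.* The flag is a sponsor-defined label and does not estimate a defined quantity. The documents give no event rate, so no distortion of a result can be shown. What can be shown is insensitivity.
- *The SAP contradicts the protocol.* Entry caps and abnormality flags serve different purposes.

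It can also be said that every row of Attachment 3 is fixed across ages. True, but age matters far more for creatinine: its entry caps differ by 106/44 = 2.41-fold, against 90/80 = 1.13-fold for the hemoglobin entry limits.

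**Conclusion.** The point holds as a minor one. As written, the rule cannot flag a subject who enters at age 2–5 below a 3.01-fold rise, or one who enters at age 6–10 below a 2.14-fold rise. The 66% condition can decide alone only for subjects aged 11 or over at entry.

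This rests on baseline respecting the criterion 15f caps. How much the other summaries compensate depends on whether the reference ranges are age-specific, which the documents leave open. The effect is confined to descriptive safety output. The PK endpoints are untouched and no hypothesis test is involved.

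**What to change.** In the creatinine row of SAP Attachment 3, keep the 66% condition and replace the absolute condition with: **value > the lower of 132.6 µmol/L and 1.5 × the age-specific ULN, by age at sampling**. State in SAP 6.3 that age-specific reference ranges, not generic ones, are used for creatinine.

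Taking the lower of the two limits matters. The documents give no creatinine ULN. If, for illustration, ULN equals the entry cap, 1.5 × ULN is 66, 93, 132 and 159 µmol/L across the four bands. Used alone, 159 would lose an adolescent going from 80 to 150 (1.88-fold), who is flagged today. If the ULN at 13 and over were 88, the limit would be 132, almost unchanged. With the lower-of rule, no age group loses sensitivity in either case. Under the same illustration, a child aged 2–5 at the cap is flagged at 1.66-fold (73.0 > 66), the 40-to-120 child is flagged, and a baseline of 25 needs 66/25 = 2.64-fold instead of 5.30-fold.

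Age at sampling is needed because follow-up to Week 252 spans 252/52 = 4.8 years, enough to move a child between bands.

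The cost is one SAP cell, one sentence, minor programming and a few more flags in young children. If the tables have already been produced, a supplementary listing of rises of 66% or more in subjects aged 2–10 at entry would serve.
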